### **3.3 Rationale of dose/regimen, duration of treatment**

The dose and dosing regimen of fingolimod 0.5 mg once a day has been identified in the phase III development program of fingolimod in RRMS as providing the best benefit/risk ratio and is therefore the proposed dose and regimen in the registration files to the health authorities and is the approved dose where fingolimod has been registered.

The duration of treatment of a patient in this trial is dependent on which study the patient participated in previously as well as the availability of reimbursement for commercially available fingolimod in the respective country. The end of the study is planned for 30 June 2018 (+/- 3 months). Individual patient's end of treatment visits should occur at their routine 6 monthly scheduled visit closest to 30 June 2018 to ensure all patients complete within the window for the end of the study.

Patients participating in this study will provide clinical data of 7-15 years of exposure, which will provide information on the long-term safety, tolerability and efficacy profile to help in therapeutic decision making.

[Only in the UK and Poland: The duration of treatment of a patient in this trial is dependent on what study the patient participated in previously (phase II/III vs. other). Phase II/III patients will remain in the study maximally through 30-Jun-2016. Patients, who participated in any designated global fingolimod MS trial other than phase II/III (e.g. CFTY720D2316, CFTY720D2320, etc.), were allowed to remain in the study until the drug was registered and through approximately one-year post approval or maximally through 31-Dec-12.]

[Only for Norway: The duration of treatment of a patient in this trial ran for approximately 12 months following the completion of the previous fingolimod trial or maximally through 01-Aug-2012.]

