#### **6.4.2 Expanded Disability Status Scale (EDSS)**

EDSS will be determined only during Study Part One, based on neurological examination at scheduled visits according to [Table 6-1](#) and in the setting of a suspected MS relapse.

EDSS is a scale for assessing neurologic impairment in MS. It is a two-part system including: (1) a series of scores in each of eight functional systems, and (2) the EDSS steps (ranging from 0 (normal) to 10 (death due to MS)). The functional systems are Visual, Brain Stem, Pyramidal, Cerebellar, Sensory, Bowel and Bladder, Cerebral and other functions. It is recommended that fatigue will not be included into the Cerebral score of the EDSS.

For patients coming from phase II/III studies, EDSS will be assessed by a treating physician who has been EDSS trained. A one-time Neurostatus certification is required for all evaluating physicians who have patients enrolled from phase II/III studies. If a new rater is brought on board at any time throughout the study, proof of certification of that rater will be required at that time before any EDSS assessments can be done by the new rater. A certified backup evaluating physician should be appointed to conduct neurological examination ONLY when the primary evaluating physician is unavailable due to illness, vacation, or travel. Blinding of the evaluators is not required in this protocol and the PI can serve as the rater provided training requirements have been met.

For patients who transferred from trials other than the phase II/III trials, the individual functional scores do not need to be collected, and the evaluating physician performing EDSS assessments does not have to carry a certification.

EDSS assessments are detailed in [Table 6-1](#). Refer to [Appendix 8](#) for information on Expanded Disability Status Scale (EDSS).

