2.5 Analysis sets

The following analysis sets will be defined.

- **Enrolled set:** The enrolled set will include all patients who entered the long-term follow-up study part I (excludes long-term follow-up study screen failures), but will exclude patients with protocol deviation severity code of 8 (8=exclude from all analyses) in the long-term follow-up study part I.
- **Safety set:** The safety set will include all patients who entered the long-term follow-up study part I and received at least one dose of fingolimod in any study, but will exclude patients with protocol deviation severity codes of 5 (5=exclude from all safety analyses) and 8 (8=exclude from all analyses) in the long-term follow-up study part I. Note that all data reported in the long-term follow-up study part I will be analyzed, including assessments or events which started before the long-term follow-up study part I.
- **Fingolimod safety set:** The fingolimod safety set will include all patients who entered the long-term follow-up study part I and received at least one dose of fingolimod in any study, but will exclude patients with protocol deviation severity codes of 5 (5=exclude from all safety analyses) and 8 (8=exclude from all analyses) during the core study prior to entry to the long-term follow-up study part I. For patients with such protocol deviations after the core study, record level data associated with the protocol deviations will be excluded from the analysis.

- **Fingolimod full analysis set:** The fingolimod full analysis set will include all patients who entered the long-term follow-up study part I and received at least one dose of fingolimod in any study but will exclude patients with protocol deviation severity codes of 0 (0=exclude from all efficacy analyses) and 8 (8=exclude from all analyses) during the core study prior to entry to the long-term follow-up study part I. For patients with such protocol deviations after the core study, record level data associated with the protocol deviations will be excluded from the analysis.
- **Follow-up set:** The follow-up set will consist of all patients in the safety set who have any follow-up visit data or at least one safety record after the study drug discontinuation. It will be used for summary of adverse events and concomitant medications with occurrences after last dose of fingolimod only.

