2.5.1 Subgroups

The following subgroups are defined for AE analysis:

1. Duration of fingolimod treatment up to the end of the long-term follow-up study part I (yearly interval):
 - Year 1 subgroup: patients on fingolimod treatment ≥ 0 year (≥ 1 day)
 - Year 2 subgroup: patients on fingolimod treatment ≥ 1 year (≥ 360 days)
 - Year 3 subgroup: patients on fingolimod treatment ≥ 2 year (≥ 720 days)
 - Year 4 subgroup: patients on fingolimod treatment ≥ 3 year (≥ 1080 days)
 - Year 5 subgroup: patients on fingolimod treatment ≥ 4 year (≥ 1440 days)
 - Year N subgroup: patients on fingolimod treatment $\geq N - 1$ year ($\geq (N - 1) \times 360$ days)
2. Patients from Phase II/III studies: This subgroup includes patients who have enrolled in any of the following studies: D2201, D2301, D2302, and D2309 before entering the long-term follow-up study part I.

3 Patient Disposition

All screen failures in the long-term follow-up study will be listed along with their primary reason for failing screening.

The number and percentage of patients who completed the long-term follow-up study part I, and who discontinued the long-term follow-up study part I, along with the primary reason for discontinuation, will be summarized for the enrolled set. The number and percentage of patients who are expected to have follow-up visits and who returned for 3-month and 6-month follow-up visits will also be summarized.

The patients who discontinued from the long-term follow-up study part I and corresponding reasons will be listed for the enrolled set. Additionally, a similar listing will be provided for the enrolled set of patients from D2312 and D2402 studies who discontinued early from the long-term follow-up study part I.

4 Protocol Deviations

The number and percentage of patients in the enrolled set with each protocol deviation in the long-term follow-up study part I will be displayed by protocol deviation category. Additionally, patients with at least one protocol deviation during the long-term follow-up study part I and patients with at least one protocol deviation causing exclusion from any analysis set (deviation severity codes 0, 5, or 8) will be summarized.

The protocol deviation data will be listed as well.

Additionally, the investigator comments during the long-term follow-up study part I will be listed.

5 Background and demographic characteristics

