5.3 MS disease history characteristics before enrollment in core study

Using data collected from the patient's core study, the following MS disease history characteristics will be summarized for the enrolled set: duration of MS since diagnosis in years, duration of MS since first symptoms in years, number of relapses in the last year prior to enrollment in the core study, number of relapses in the last 2 years prior to enrollment in the core study, time since the onset of the most recent relapse (in months) prior to enrollment in the core study, and duration from MS diagnosis date to last dose date of study drug (in years). The baseline EDSS score and the duration of exposure to fingolimod prior to first dose in the long-term follow-up study part I will also be summarized for the enrolled set. Note that not all parameters are collected across all studies.

The following definitions will be used in calculations involving MS disease history characteristics: one year is defined as 365.25 days and one month is defined as 30 days.

For the MS disease history summary, the variable *Duration of MS since diagnosis* (years) will be derived for each patient as: (first dose date of any study drug among all studies a patient has participated in – the MS diagnosis date + 1)/365.25. *Duration of MS since first symptom* (years) is calculated as (first dose date of any study drug among all studies a patient has participated in – the first MS symptom date + 1) / 365.25. The *time since the onset of the most recent relapse* (months) is computed as (first dose date of any study drug among all studies a patient has participated in – the most recent relapse onset date prior to enrollment in the core study + 1)/30. The duration from MS diagnosis date to last dose date of study drug (in years) is calculated as (last dose date of any study drug among all studies a patient has participated in - the MS diagnosis date + 1)/365.25. Note that the first dose date of any study drug among all studies a patient has participated in may not be fingolimod.

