8.1.4 MS relapses analyses

MS relapses analyses will be conducted on the fingolimod full analysis set. All analyses will be done for all relapses (confirmed and unconfirmed) and for confirmed relapses.

A summary of ARRs will be presented by time period (cumulative time intervals: ‘Month 0 to Month 6’, ‘Month 0 to Month 12’, ‘Month 0 to Month 24’, ‘Month 0 to Month 36’, ... incremented by 1 year for each successive interval, plus ‘Month 0 to end of study treatment’ and ‘Month 0 to end of follow-up’) from first dose of fingolimod among all studies. The summary will include number of patients summarized, number of relapses, time in study (days), and group level ARR. In addition, model based estimates of ARR and corresponding two-sided 95% confidence interval will be obtained by fitting a negative binomial regression model adjusted for the number of relapses in the last two years prior to

enrolment in the core study and EDSS score at first dose of fingolimod baseline, with the logarithm of the time in study as the offset variable.

A summary of relapse characteristics will be displayed by time period (consecutive yearly intervals: 'Month 0 to Month 12', 'Month 12 to Month 24', etc., plus 'End of study treatment to End of follow-up') from first dose of fingolimod among all studies. Relapse characteristics will be summarized at a patient level (the number and percent of patients with at least one relapse type) and at a relapse event level (the number and percent of a particular type of relapse out of the total number of relapses). The types of relapses being summarized include: relapses which affect daily activities, relapses which require steroids, and relapses which require hospitalization.

The time to first onset of relapse from first dose date of fingolimod among all studies will be analysed. Specifically, the number of patients at risk, the cumulative number of patients with relapse, the Kaplan-Meier (KM) estimate of the percent of patients without relapse and corresponding standard error and two-sided 95% CI will be provided at each yearly time point (1 year = 360 days). Patients with no relapse, patients for whom follow-up ends before a confirmed relapse occurs, and patients who drop out prior to the relapse will all be censored, i.e. the time to event for these patients will be the time in study (from first dose of fingolimod among all studies to last available visit/evaluation date across all panels).

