8.3 Analysis of EDSS scores

The EDSS scores are used for the confirmation of MS relapse and the confirmation of disability progression. All EDSS summaries are based on the fingolimod full analysis set.

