If the first scheduled visit after ≥ 166 days for a “6-month confirmed disability progression” does not meet the conditions above, the subsequent scheduled visits will be checked until a confirmation visit is found. If a confirmation visit cannot be found, then above process will be repeated to look for the next disability progression onset and its confirmation visit or until it is certain that no confirmation visit can be found for the progression onset.

A patient is considered to have a 6-month confirmed disability progression if a progression onset with a confirmation visit is found. Otherwise, the patient is considered not to have a 6-month confirmed disability progression and will be referred to as a censored patient.

If a patient died due to MS (EDSS=10), he or she will be considered to have a 6-month confirmed disability progression, irrespective of the EDSS at the reference time point or the change in EDSS.

The time to first 6-month confirmed disability progression from first dose of fingolimod among all studies until the end of the long-term follow-up study part I will be summarized in a yearly interval for fingolimod full analysis set. Specifically, the number of patients at risk, the cumulative number of patients with event, the Kaplan-Meier (KM) estimate of the percent of patients without 6-month confirmed disability progression and corresponding standard error and two-sided 95% CI will be provided at each yearly time point (1 year = 360 days).

A Kaplan-Meier plot of time to first 6-month confirmed disability progression from first dose of fingolimod among all studies to the end of long-term follow-up study part I will be presented.

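### Relapse and EDSS analyses pool source cohorts that collected different data: confirmed-relapse results include time with no recordable event, and SAP 8.3.3 leaves its risk set and censoring date open

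*SAP*

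**What the plan says.** **Population.** SAP Part I, 8.3: "All EDSS summaries are based on the fingolimod full analysis set". Section 8.1.4: "MS relapses analyses will be conducted on the fingolimod full analysis set". Section 2.5 defines that set: "The fingolimod full analysis set will include all patients who entered the long-term follow-up study part I and received at least one dose". The dose may come from whichever trial, and certain core-study deviations lead to exclusion. No EDSS is required. Section 2.5.1 defines a phase II/III subgroup under "The following subgroups are defined for AE analysis". It is also used for demographics (5.2) and exposure (6.1), but not for relapse or EDSS.

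**Data collection by cohort.** For patients from outside phase II/III, Protocol 6.4.2 says "the individual functional scores do not need to be collected, and the evaluating physician performing EDSS assessments does not have to carry a certification". SAP 8.3.1 nevertheless summarises functional system scores on the full set. SAP 8.1.2 says that D2399 does not collect relapse confirmation for these patients. It adds that D2316, D2320, D2399E1 and D2399 before Amendment 4 did not collect it at all, and that uncollected confirmation counts as unconfirmed.

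**Relapse analyses.** Section 8.1.4 runs every relapse analysis twice, for all relapses and for confirmed relapses. In the Kaplan-Meier analysis, event-free patients are censored at their last available visit.

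**Progression.** Section 8.3.3 measures change from the EDSS before first fingolimod dose (the FDF baseline). For a patient with no confirmation visit: "Otherwise, the patient is considered not to have a 6-month confirmed disability progression and will be referred to as a censored patient". After listing baseline EDSS and relapse history, section 5.3 warns: "Note that not all parameters are collected across all studies".

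**The concern.** Two things can go wrong when cohorts with different data collection share one risk set.

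First, a patient whose relapses can never be classed as confirmed still adds follow-up to the confirmed-relapse denominator and still stands in the Kaplan-Meier risk set. This pulls the rate down and the relapse-free percentage up, for a reason unrelated to treatment.

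Second, progression is a change from the FDF baseline. A patient with later EDSS scores but no such baseline cannot meet the change criterion, death from MS aside. Section 8.3.3 does not say whether that patient is in the risk set, or until when.

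Long-term efficacy is the stated secondary objective, and these curves and rates are its main output. With no phase II/III display, a reader cannot see how much of a long-term figure comes from patients with certified EDSS and confirmed relapses.

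**Working it through.** The plan gives no cohort sizes, event rates or share of patients without an FDF EDSS, so there is no planned figure to reproduce. The rules are compared first. The calculations after that rest on stated assumptions.

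**1. Section 8.3.2 against 8.3.3**
- Baseline: 8.3.2 admits only patients whose baseline EDSS is below the threshold, so a missing baseline removes the patient. 8.3.3 sets no baseline condition.
- Censoring date: 8.3.2 uses the last EDSS date, or Day 1 if there is no post-baseline EDSS. 8.3.3 gives none.
- Exposed case: later EDSS but no FDF EDSS, in 8.3.3 only. It is possible because Table 6-1 codes baseline EDSS as S1. Under Protocol section 6, an S1 assessment not done in the previous trial is done at D2399 baseline, which for a patient already on fingolimod is after first dose.

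**2. Confirmed ARR**
Let f be the share of person-time without confirmation, with the same true rate throughout. Reported rate = true rate × (1 − f). Assuming a true rate of 0.20 per year:
- f = 10%: 0.20 × 0.90 = 0.18
- f = 25%: 0.20 × 0.75 = 0.15
- f = 40%: 0.20 × 0.60 = 0.12

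**3. Confirmed-relapse Kaplan-Meier**
Pooled hazard at time t = sum(at risk × hazard) / sum(at risk), where patients outside phase II/III are at risk with recordable hazard 0. Assumptions: hazard 0.20 per year in phase II/III; others leave uniformly between 0.5 and 3 years; phase II/III patients leave uniformly between 3 and 10 years. Two-year relapse-free percentage:
- phase II/III alone: exp(−0.20 × 2) = 67.0%
- pooled, 30% from outside phase II/III: 75.0%
- pooled, 50% from outside phase II/III: 81.1%

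**4. Progression under 8.3.3**
Same method. Assumptions: hazard 0.04 per year in both cohorts; 30–70% from outside phase II/III, leaving uniformly from 0.5 to 3 or 5 years; phase II/III exit as in step 3. Five-year progression-free percentage:
- true value: exp(−0.04 × 5) = 81.9%
- half of the other cohort without FDF EDSS, kept to last EDSS: 82.8–86.5% (about +1 to +5 points)
- all of the other cohort without FDF EDSS, kept to last EDSS: 83.8–91.2% (about +2 to +9 points)
- the same patients excluded or censored at Day 1: 81.9%, no shift

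Length of stay matters too. Take a hazard of 0.05 per year and a share m of the risk set without FDF EDSS, with a true 8-year value of exp(−0.4) = 67.0%.
- Kept at risk all 8 years, m + (1 − m) × exp(−0.4): 68.7%, 70.3% and 73.6% for m = 5%, 10% and 20%.
- Leaving at 2.5 years, [m + (1 − m) × exp(−0.125)] × exp(−0.275): 67.5%, 67.9% and 68.8%, or about +0.4, +0.9 and +1.8 points.

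**5. Pooling with everyone assessable**
Under the step 4 assumptions, equal hazards give 81.9% for both the pooled and the phase II/III curve. With 0.025 to 0.06 per year outside phase II/III, the pooled value runs from 85.2% down to 77.8%.

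**6. Two ARR estimates on different patients**
The negative binomial model in 8.1.4 adjusts for FDF EDSS and two-year relapse history. Protocol 9.4.2 imputes no missing values, so a standard fit drops patients lacking either covariate. The group-level ARR in the same summary keeps them.

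**The case against.** - **The population follows the protocol.** Protocol 9.5.1 gives efficacy estimates for patients with at least one fingolimod dose, and 9.4.3 names the phase II/III subgroup for adverse events. The study is descriptive, with no tests. This stands: the full set should remain, and making phase II/III the main display would be a trade-off against 9.5.1. It does not prevent an added display.
- **The SAP already discloses the relapse problem.** Section 8.1.2 says uncounted time can make the ARR look low and prefers the all-relapse rate. This stands for the ARR. It does not reach the confirmed-relapse Kaplan-Meier curve, which has the same flaw and no caveat.
- **Missing FDF EDSS is not shown.** S1 presumes that EDSS was done in the previous trial. For a patient first dosed in D2399, a pre-dose baseline EDSS is the FDF baseline. Section 5.3's note does not say that any study failed to collect EDSS. This stands, so the 8.3.3 point is conditional.
- **Reading 8.3.3 as counting unassessable patients as progression-free.** A reader might infer this, but the rule calls them censored. Section 8.3.2 handles both missing cases, and the bias in 8.3.3 depends on a censoring date that is not given.
- **A shorter stay for phase IIIb patients.** Protocol 3.3 says "The duration of treatment of a patient in this trial is dependent on which study the patient participated in previously", then adds availability of reimbursement. An explicit earlier limit for patients from outside phase II/III is current text only for the UK and Poland. The general phase IIIb endpoint appears only in the amendment log.

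**Conclusion.** The concern holds in three parts.

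**Confirmed relapse.** As written, the rules bias confirmed-relapse results in a favourable direction, through follow-up in which no confirmed event can be recorded. The ARR falls in proportion to the uncollected share of person-time, and the Kaplan-Meier curve is too high. The figures in steps 2 and 3 show the mechanism under assumed rates and shares; they do not estimate this trial.

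**Progression (8.3.3 only).** The risk set and censoring date are undefined for patients with later EDSS but no FDF baseline. If such patients exist and stay at risk to their last EDSS, progression-free estimates are biased upward by an amount the documents do not allow to be computed. If they are excluded or censored at Day 1, the bias is zero. The EDSS 4/6/7 analyses are not affected.

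**No phase II/III display.** Rater certification, functional scores and relapse confirmation differ by cohort, and no planned efficacy display separates them. A reader might go further and infer that the pooled late curve describes neither cohort. That needs progression risk to differ by source trial, or the 8.3.3 gap to operate. With equal hazards and proper exclusion the two curves agree (step 5), and the documents give no rates by cohort. No direction or size can be given for the effect of uncertified raters.

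**What to change.** 1. **Section 8.3.3.** Limit the risk set to patients with an FDF baseline EDSS. Apply the 8.3.2 censoring rule: last EDSS date, or Day 1 if there is no post-baseline EDSS. Print the number excluded by source cohort.
2. **Sections 8.1.4 and 8.3.1–8.3.3.** Add displays for the phase II/III subgroup of 2.5.1 beside the full analysis set. Limit the confirmed-relapse ARR and Kaplan-Meier to patients and time in which confirmation was collected. For Kaplan-Meier, state how a gap is treated, since phase II/III patients also have time without confirmation in D2399 before Amendment 4 and in D2399E1. Censoring at the start of the first gap is simplest but shortens follow-up; the all-relapse curve still covers the full horizon.
3. **ARR.** Keep the covariate-adjusted negative binomial model, which Protocol 9.5.1.1 requires; an offset-only model would depart from it. Also give the crude ARR on the model's patients, and print N for both.

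The cost is SAP wording and one more run of existing programs. The added displays contain fewer patients, and the confirmed-relapse analyses use fewer patients and less follow-up.
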